4. STATISTICAL ANALYSES

The primary analysis will occur when the last enrolled patient from the global enrollment phase has completed the study. Significance testing of the primary and secondary endpoints will account for multiplicity and control family-wise type I error, which is fixed at 0.05 two-sided. The study has one single primary efficacy endpoint (absolute change from baseline at Week 52 in FVC [mL]) and one family of secondary efficacy endpoints that have been ordered in a prespecified sequence, starting with the key secondary endpoint, absolute change from baseline at Week 52 in 6MWD (see Section 4.4).

The planned statistical analysis will control the overall type I error for the testing of these efficacy endpoints by applying a fixed-sequence multiple testing strategy, testing all the endpoints according to the pre-specified order. All hypothesis tests will be two-sided unless otherwise specified.

4.1 GENERAL CONSIDERATION

The efficacy endpoints comprise one primary endpoint (FVC [mL]), one key secondary endpoint (6MWD [m]), a series of other secondary endpoints and other exploratory endpoints. All efficacy analyses will be performed on the FAS population, unless otherwise specified. Participants will be analyzed according to the treatment assigned at randomization by IxRS. Significance testing of the primary and secondary endpoints will account for multiplicity and control family-wise type I error, which is fixed at 0.05 two-sided. All safety analyses will be performed in the safety-evaluable population, unless otherwise specified. Participants will be analyzed according to the treatment they actually received.

In safety analyses, all deaths are included, from all sources, regardless of completeness of death date; participants who died with only a partial death date available will be included. In efficacy analyses, death data from adjudication will be used. If the death date is only partially available, the missing part of the date will be imputed.

For hospitalization in efficacy analyses, the adjudicated date of hospitalization will be used and a partial date will be imputed using the same approach as for death.

4.2 PARTICIPANT DISPOSITION

The number of patients randomized will be tabulated by region, country, study site and treatment arm. The FAS, safety-evaluable, PK-evaluable and PRO-evaluable populations, including numbers of patients in each population, will be summarized. Patient disposition (the number of patients treated and have completed the study) will be tabulated by the treatment arm. Premature treatment discontinuation and study discontinuation, as well as reasons for discontinuations, will be summarized.

4.3 PRIMARY ENDPOINT(S) ANALYSIS

4.3.1 Definition of Primary Endpoint(s)

The primary efficacy endpoint is the between-group difference in the mean absolute change from Baseline (Dosing Day 1) at Week 52 in FVC (mL). The comparison of zinpentraxin alfa with placebo will be analyzed at a 0.05 two-sided significance level.

All FVC mL measurements that meet the minimal level of quality will be used for the primary analysis, except those recorded after lung transplantation, whatever other intercurrent events might have occurred before that were recorded. No imputation for missing data is planned to be performed for the primary analysis since the primary analysis assumes missing data are MAR and the planned analysis model is unbiased under this assumption.

4.3.2 Main Analytical Approach for Primary Endpoint

Descriptive statistics for the raw values at each visit and the change from baseline at each visit through Week 52 in FVC mL will be computed by treatment group for the FAS population.

The comparison of zinpentraxin alfa with placebo will be carried out via a linear mixed (random coefficient) model at a 0.05 two-sided significance level. Each subject's vector of responses is independent of the other subjects, and within-subject responses are correlated.

The statistical model can be written as follows:

$$Y_{ij} = (\beta_0 + \beta_{0i}) + (\beta_1 + \beta_v Trt_i + \beta_{1i}) * t_{ij} + \beta_s Sex_i + \beta_a Age_i + \beta_h Height_i + \beta_c StrataC_i + \beta_r StrataR_i + \epsilon_{ij}$$

where

- Y_{ij} is the FVC (mL) value for subject i at visit j (including baseline);
- β_0 and β_1 are the intercept and the slope;
- β_{0i} and β_{1i} are the random subject effects for intercept and slope;
- $Trt_i = 0$ if subject i is in the Placebo group and $Trt_i = 1$ if subject i is in the zinpentraxin alfa group;
- β_v is the coefficient for the interaction term of treatment effect and assessment time;
- t_{ij} is the assessment time (continuous in days) for subject i at visit j ;
- β_s , β_a and β_h are the coefficients for subject specific demographic variables;
- Sex_i , Age_i , and $Height_i$ are the sex (male as the class of reference), baseline age (years) and baseline height (cm) for patient i ;
- β_c and β_r are the coefficients for subject specific stratification variables;
- $StrataC_i$ and $StrataR_i$ are the stratification factors on concurrent IPF treatment (no concurrent IPF treatment as the class of reference) and region (Rest of World as the class of reference) for subject i ;
- ϵ_{ij} is the within-subject random error for subject i at visit j ;
- β_{0i} and β_{1i} are assumed to have a multivariate normal distribution with mean 0 and unstructured covariance matrix;
- ϵ_{ij} are assumed to be independent and normally distributed with mean 0 and variance σ_ϵ^2

If there are convergence problems with the model, the following covariates will continue to be removed from the model (in this order) until convergence is met (1) stratification factor for region, (2) stratification factor for concurrent IPF treatment (3) age, sex, and height. If the model still fails to converge, a random intercept model will be used (no random slope).

The comparison of zinpentraxin alfa with placebo will be carried out by estimating the difference in mean absolute change from baseline at Week 52 between the two treatment arms with 95% CI and p-value.

4.3.3 Sensitivity Analyses for Primary Endpoint

4.3.3.1 Sensitivity Analysis Addressing the Effect of Missing Data After Death due to IPF

To analyze the effect of missing data after death, a rank analysis of covariance (ANCOVA) model will be fit, where patients who die are assigned the worst rank. Specifically, for each patient who survives the duration of the trial, a slope will be calculated from a line fit through their observed FVC assessments. The slopes will then be ranked, assigning the worst rank to patients who die. The rank ANCOVA model will include age, sex, height and ranked baseline score as covariates.

4.3.3.1.1 Sensitivity Analysis Addressing the Effect of Missing Data After Treatment Discontinuation

Patients are expected to continue with study assessments after permanent treatment discontinuation. However, it is possible that patients who discontinue treatment fail to return for their follow-up assessments or discontinue the study, in which case some post-discontinuation data would be missing. Analysis under MAR will implicitly impute these missing values based on all observed data without distinguishing between on-treatment and off-treatment data and may therefore overestimate the treatment effect. Furthermore, the ICE strategy for treatment discontinuation would be a hybrid between a hypothetical and treatment policy strategy, and it becomes unclear what treatment effect is actually being estimated.

More conservative imputation approaches will be implemented to assess the sensitivity of treatment effect estimation and inference to missing data assumptions. The first approach will be to use conditional mean imputation for reference-based imputation of missing data ([Wolbers et al. 2022](#)). The imputation model will be an MMRM with baseline outcome, age, sex, height, treatment group, visit and treatment-by-visit interactions as covariates. Missing data for patients in the placebo arm will be imputed under MAR, and missing data for patients in the zinpentraxin alfa arm will be imputed under copy increments in reference. Under this reference-based assumption, patients in the intervention arm who discontinue treatment do not get any further benefit from treatment after discontinuation. The imputed, complete data will be analyzed via ANCOVA, with FVC (mL) slope as the outcome and baseline FVC, age, sex, height and treatment as covariates. Re-sampling based inference for the treatment effect estimate will be obtained via the jackknife.

In addition to the reference-based imputation, a tipping point analysis will be implemented by applying different delta-adjustments for each treatment group to the imputed data to see which combination of delta values tip the primary analysis result.

4.3.3.1.2 Sensitivity Analysis Addressing Non-linearity

To evaluate the impact of assuming a linear disease trajectory, a repeated measures mixed-effects model (MMRM) will be used to estimate the difference in mean change from baseline in FVC (mL) at Week 52. For this sensitivity analysis, only data from scheduled assessments will be used to fit the MMRM. The response variable for the model is change from baseline in FVC (mL). The following variables will be included as model terms: baseline FVC (mL), stratification factors, treatment group, visit and treatment-by-visit interaction. Subject, treatment, and visit will be class variables and the within-subject errors will be assumed to have an unstructured variance-covariance matrix. If the analysis fails to converge, the following covariance structures will be tested: compound symmetry, first-order autoregressive [AR(1)], and Toeplitz. The covariance structure converging to the best fit, based on Akaike's information criterion (AIC), will be used.

The difference in the least squares mean change from baseline between the zinpentraxin alfa and placebo groups will be estimated at each post-baseline visit, as well as 95% CI's and p-values. The MMRM LS means plot with CI's will be made to visualize the estimates.

4.3.4 Supplementary Analyses for Primary Endpoint(s)

4.3.4.1 Subgroup Analyses for Primary Endpoint(s)

The generalizability of primary endpoint results when comparing zinpentraxin alfa to placebo will be investigated by estimating the treatment effect in subgroups based on stratification factors and key baseline demographics, disease characteristics, etc., as listed in [Table 6](#).

Descriptive summaries including number and proportion of patients in each category will be provided overall and by treatment group as appropriate. Summaries of primary endpoint by these subgroups will be provided in forest plots.

Table 6 Subgroup Definitions

Patient Characteristics	Categories
Baseline concomitant medications	
 – Concurrent use of either nintedanib or pirfenidone treatment – Concurrent use of nintedanib treatment – Concurrent use of pirfenidone treatment – No concurrent treatment
Geographic region	
 China North America Europe Latin America Rest of World
Age	
 < 65 years 65 to < 75 years ≥ 75 years
Sex	
 Female Male
zinpentraxin alfa generation	
 First Generation Second Generation

4.4 SECONDARY ENDPOINTS ANALYSES

If the primary efficacy test on FVC mL is found significant at the alpha level of 0.05 two-sided then the fixed-sequence testing procedure will continue by testing the secondary endpoints in a hierarchical manner as specified below:

1. Absolute change from baseline at Week 52 in 6MWD (m)
2. Absolute change from baseline at Week 52 in FVC% predicted
3. Time to disease progression, defined as time to first occurrence of ≥ 10% absolute decline in % predicted FVC, ≥ 15% relative decline in 6MWD, or death
4. Time to first respiratory-related hospitalization
5. Absolute change from baseline at Week 52 in University of California, San Diego-Shortness of Breath Questionnaire (UCSD-SOBQ)
6. Absolute change from baseline at Week 52 in St. George Respiratory Questionnaire (SGRQ) Total Score
7. Time to first acute exacerbation of IPF, or suspected acute exacerbation of IPF, as determined by the Clinical Adjudication Committee
8. Absolute change from baseline at Week 52 in hemoglobin (Hgb)-corrected DL_{CO} % predicted
9. Survival, as measured by all-cause mortality

4.4.1 Key/Confirmatory Secondary Endpoint

The assessment of the key secondary endpoint (6MWD [m]) using the 6MWT is described in Section 4.5.7 of Protocol.

It will be analyzed using the same estimand strategy, descriptive statistics, and model as the primary endpoint (FVC [mL]) in Section 1.1 and Section 4.3.2 and will be analyzed at a 0.05 two-sided significance level.

Subgroup analyses for the primary efficacy endpoint described in Section 4.3.4.1 will be performed for the key/confirmatory secondary endpoint as well using the same descriptive summaries and summaries of treatment effect in forest plots.

4.4.2 Supportive Secondary Endpoint(s)

4.4.2.1 Other Continuous Secondary Endpoints

The other continuous secondary endpoints include:

- absolute change from baseline at Week 52 in FVC% predicted
- absolute change from baseline at Week 52 in Hgb-corrected DL_{CO} % predicted

FVC% predicted will be analyzed using the same estimand strategy, descriptive statistics and model (excluding age, sex and height as covariates) as the primary endpoint (FVC [mL]) in Section 1.1 and Section 4.3.2 and will be analyzed at a 0.05 two-sided significance level.

Visit summary and change from baseline analyses will be performed for Hgb-corrected DL_{CO} % predicted values. Summary statistics (number of patients, mean, standard deviation, median, minimum, maximum) of absolute values and changes from baseline at each time point will be presented by treatment arm. Hgb-corrected DL_{CO} % predicted will be analyzed using the same estimand strategy as the primary endpoint (FVC [mL]) in Section 1.1.

A MMRM will be used for comparing the least squares mean change from baseline at Week 52 in Hgb-corrected DL_{CO} % predicted values between treatment arms at a 0.05 two-sided significance level. The model will include baseline value as a covariate, and treatment, time, stratification variables and treatment by time interaction as explanatory variables. Repeated measures over time will be accounted for by an unstructured covariance structure.

The statistical model is as follows:

$$Chg_{ij} = \beta_0 + \beta_t Trt_i + \beta_v Visit_j + \beta_r Trt_i * Visit_j + \beta_b Base_i + \beta_c StrataC_i + \beta_r StrataR_i + \varepsilon_{ij}$$

where

- Chg_{ij} is the change from baseline for subject i at visit j ;
- β_0 is the intercept;
- β_t is the coefficient for the treatment effect and Trt_i is the planned treatment for subject i : $Trt_i = 0$ if subject i is assigned to the Placebo group ($k = \text{Placebo}$) and $Trt_i = 1$ if subject i is assigned to the zinpentraxin alfa group;
- β_v is the coefficient for the visit effect and $Visit_j$ is the categorical visit;
- β_r is the coefficient for the interaction term between treatment and categorical visit and $Trt_i * Visit_j$ is the interaction term between treatment and categorical visit;
- β_b is the coefficient for the baseline measure and $Base_i$ is the baseline measure for subject i ;
- β_c and β_r are the coefficients for subject specific stratification variables;
- $StrataC_i$ and $StrataR_i$ are the stratification factors on concurrent IPF treatment (no concurrent IPF treatment as the class of reference) and region (Rest of World as the class of reference) for subject i ;
- ε_{ij} is the random error for subject i at visit j .

If the analysis fails to converge, the following covariance structures will be tested: compound symmetry, first-order autoregressive [AR(1)], and Toeplitz. The covariance structure converging to the best fit, based on Akaike's information criterion (AIC), will be used.

The least squares mean estimates of the mean change from baseline and the difference between the two treatment arms at each post-baseline visit will be provided with 95% CIs and p-values.

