1.2 STUDY DESIGN

Study WA42293 is a Phase III, randomized, double-blind, placebo-controlled, pivotal clinical trial designed to confirm the efficacy and safety of zinpentraxin alfa in the treatment of IPF patients with or without concurrent treatment with pirfenidone or nintedanib.

Approximately 658 patients will be randomly assigned on a 1:1 basis to treatment with zinpentraxin alfa at a dose of 10 mg/kg or matched placebo on Days 1, 3, and 5, then one infusion every 4 weeks (Q4W) for 48 weeks. Patients will be evaluated for study eligibility during a screening period of up to 4 weeks. Study treatment will be administered by intravenous (IV) infusion over 50–70 minutes every 4 weeks. If any infusions are missed, repeat loading doses will be required at the next scheduled visit (three doses administered on alternate days). During the placebo-controlled treatment period (defined as Day 1 to Week 52), patients will continue to receive blinded study treatment every 4 weeks to Week 48 and have a final assessment visit at Week 52.

[figure not shown]
This study will enroll approximately 658 patients globally across all sites. Enrollment will be globally competitive. After completion of the global enrollment phase, additional patients may be enrolled in an extended China enrollment phase at sites in mainland China, Hong Kong, and Taiwan. The global population will include all patients enrolled during the global enrollment phase and the China subpopulation will include all patients enrolled at sites in mainland China, Hong Kong, and Taiwan (i.e., during both the global

enrollment phase and the extended China enrollment phase). Separate analyses will be performed for the global population and the China subpopulation (see Section 4.7.6 for China subpopulation analyses).

Following participation in this study, patients may be eligible to participate in a separate open-label extension (OLE) study (Study WA42294) to receive treatment with zinpentraxin alfa and further study assessments. Patients who do not enroll in the OLE study will be followed up for an additional 4 weeks (to Week 56, for safety monitoring). The OLE study will also consist of a long-term survival cohort, where patients who do not want further study assessments or treatment can enroll (for long-term collection of survival data only).

The study schema is shown in Figure 1.

Figure 1 Study Schema

IV=intravenous; OLE=open-label extension; Q4W=once every 4 weeks.

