2.2.1 Assumptions on Treatment Effects for Sample-Size and Power Calculations

The hypotheses on treatment effect-sizes used for sample-size and power calculations were based on the results of the placebo-controlled period of the PRM-151-202 study, summarized in Table 3.

Table 3 Results of the PRM-151-202 Study on Planned Primary and Key Secondary Endpoints

LS-Means for change from baseline at Week 28 (linear mixed effect models)				
Endpoint	Placebo (N=39) Mean (SE)	zinpentraxin alfa (N=77) Mean (SE)	Difference Mean (SE)	Standardized effect size
FVC (mL)	-242.3 (45.47)	-127.7 (32.86)	114.6 (56.10)	0.40
6MWD (meters)	-33.7 (10.52)	-0.20 (7.59)	33.5 (12.97)	0.51
FVC (% predicted)	-5.40 (0.96)	-2.50 (0.69)	2.80 (1.19)	0.46

6MWD=6-minute walk distance; FVC=forced vital capacity; SE=standard error.

The effect-sizes observed for the between-group differences in least-square means for change from baseline at Week 28 from the linear mixed effect models with random intercept and slope adjusted on stratum, were 114.6 mL for FVC mL (common standard deviation: 286.9, standardized effect-size: 0.40), 33.5 m for 6MWD (common standard deviation: 66.3, standardized effect-size: 0.51), and 2.80% for FVC % predicted (common standard deviation: 6.04, standardized effect-size: 0.46). A greater between group difference is expected at Week 52 in the current study, but a greater variability might also be observed at Week 52, due to the longer follow-up.

In the OLE of the PRM-151-202 study, where all patients received zinpentraxin alfa from Week 28 onwards, the Week 52 standard errors from the mixed model for repeated measures (MMRM) model allowed to compute corresponding standard deviations of 403.5 mL (FVC mL), 8.77% (FVC %predicted) and 82.3 m (6MWD) in patients who were initially randomized to zinpentraxin alfa, that are indeed larger than those at Week 28 (288.3 mL, 6.06% and 66.6 m respectively).

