To avoid underestimating the power of the study and to enable the opportunity to explore the efficacy in relevant patient subgroups including baseline concomitant IPF medication use, smaller standardized effect-sizes than observed in study PRM-151-202 at Week 28 of 0.25 for FVC mL and FVC % predicted and 0.30 for 6MWD were used for the calculations. In addition, to investigate the impact of increased variability for studies of longer duration, the power for this calculated sample size was assessed in the following way: (a) using the placebo-controlled treatment differences observed at Week 28 as estimates for the Week 52 treatment effects and (b) using the Week 52 standard deviations for the initially randomized zinpentraxin alfa arm from study PRM-151-202, as estimates for the Week 52 common standard deviations. This was performed in order to confirm that the nominal power is at least 80% under these assumptions.

With a total of 658 patients (329 in each arm), the nominal power to detect a standardized effect size of 0.25 for FVC mL and FVC% predicted, using a two-sided type I error level of 0.05 is 0.89 and the nominal power to detect a standardized effect size of 0.30 on 6MWD using a two-sided type I error level of 0.05 is 0.97.

With a total of 658 patients (329 in each arm), the nominal power to detect an effect of 114.6 mL on FVC mL with common standard deviation of 403.5 (standardized effect size of 0.28) using a two-sided type I error of 0.05 is 0.95. The nominal power to detect an effect of 33.5 meters on 6MWD with common standard deviation of 82.3 (standardized effect size of 0.41) using a two-sided type I error level of 0.05 is >0.99. For FVC% predicted, the nominal power to detect an effect of 2.80% with common standard deviation of 8.77 (standardized effect size of 0.32) using a two-sided type I error of 0.05 is 0.98.

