4.4.2.2 PRO Secondary Endpoints

The PRO secondary endpoints are listed below:

- Change from baseline at Week 52 in UCSD-SOBQ score
- Change from baseline at Week 52 in SGRQ total score

The PRO secondary endpoints will be analyzed using the same estimand strategy, descriptive statistics and model as Hgb-corrected DL_{CO} % predicted in Section 4.4.2.1 and will be analyzed at a 0.05 two-sided significance level.

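### If the unstructured MMRM fails to converge, the SAP falls back only on equal-variance structures, which understate the Week 52 standard error wherever variance grows over time

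*SAP*

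**What the plan says.** SAP 4.4.2.1 analyses Hgb-corrected DLCO % predicted by an MMRM with an unstructured covariance matrix. Its contingency rule reads: "If the analysis fails to converge, the following covariance structures will be tested: compound symmetry, first-order autoregressive [AR(1)], and Toeplitz". The structure with the lowest AIC among those that converge is then used. SAP 4.4.2.2 carries this model over to UCSD-SOBQ and SGRQ total, by reference to the model "in Section 4.4.2.1 and will be analyzed at a 0.05 two-sided significance level". SAP 4.3.3.1.2 repeats the rule for the MMRM that checks the linearity assumption behind the primary FVC analysis. No heterogeneous-variance version and no empirical standard error is mentioned in any of these sections.

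On variability, SAP 2.2.1 takes from the extension of the earlier study Week 52 "standard deviations of 403.5 mL (FVC mL), 8.77% (FVC %predicted) and 82.3 m (6MWD"), and describes them as "indeed larger than those at Week 28 (288.3 mL, 6.06% and 66.6 m respectively"). The same section says that variability may be greater at Week 52 because follow-up is longer. It gives no SD at any visit for DLCO, UCSD-SOBQ or SGRQ.

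**The concern.** Compound symmetry, AR(1) and Toeplitz differ in how they model correlation, but each has one variance for all visits. Week 52 is the tested visit. If it is also the most variable, a pooled variance is too low for it, so the model-based standard error is too small, the interval too narrow and the p-value too optimistic. Choosing by AIC gives no protection, because every candidate has the same restriction.

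The rule covers three formally tested secondary endpoints and one sensitivity analysis of the primary endpoint. SAP 4.7.6 also applies the methods of Sections 4.1 to 4.6 to the China and Japan subpopulations. A contingency rule should be valid in the situation it is written for.

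**Working it through.** **Inputs.** Two-sided alpha 0.05; 329 patients per arm; the SDs above, all from the SAP. From the schedule in Protocol Appendix 1, DLCO and the questionnaires have post-baseline visits at Weeks 12, 24, 36 and 52; spirometry is every 4 weeks from Week 4 to Week 52, which is 13 visits.

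**1. The plan's own figures.** Power at standardized effect 0.25: Φ(0.25 × √(329/2) − 1.96) = Φ(3.206 − 1.960) = 0.894, against 0.89 stated. The Week 28 SDs are the active-arm standard errors times √77: 32.86 × 8.775 = 288.3 mL; 7.59 × 8.775 = 66.6 m; 0.69 × 8.775 = 6.05% (6.06 stated, a rounding difference). Week 52/Week 28 SD ratios: 403.5/288.3 = 1.40; 8.77/6.06 = 1.45; 82.3/66.6 = 1.24.

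**2. Variance over time.** Only two time points are given, so a shape must be assumed. Take Var(t) = a + b·t². For FVC mL, b = (403.5² − 288.3²)/(52² − 28²) = 79,695/1,920 = 41.51, and a = 288.3² − 41.51 × 784 ≈ 50,575.

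**3. Equal-variance fit.** With complete data, the Week 52 treatment estimate is in effect the adjusted difference in Week 52 means under any of these structures, so only its standard error changes. In large samples, compound symmetry estimates the common variance as the mean of the visit variances. Hence SE ratio = √(mean variance / Week 52 variance), and type I error = 2 × [1 − Φ(1.96 × ratio)]. The mean of t² is (144 + 576 + 1,296 + 2,704)/4 = 1,180 for four visits and 1,008 for 13 visits.

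| Growth like | Visits | Mean variance | Week 52 variance | SE ratio | Type I error |
|---|---|---|---|---|---|
| FVC mL | 13 | 92,415 | 162,812 | 0.753 | 14.0% |
| FVC mL | 4 | 99,554 | 162,812 | 0.782 | 12.5% |
| FVC % predicted | 4 | 45.0 | 76.9 | 0.765 | 13.4% |
| 6MWD | 4 | 4,918 | 6,773 | 0.852 | 9.5% |

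**4. Other structures and shapes.**
- AR(1) and Toeplitz do little better. With four visits and FVC mL growth, all three ratios lie between 0.78 and 0.80 (about 12-12.5%). With 13 visits, AR(1) gives 0.762 (13.5%) and Toeplitz 0.784 (12.4%).
- Across four growth shapes (power law, linear SD, linear variance, constant plus quadratic variance) and several correlation patterns, the four-visit ranges are 11.6-13.8% (FVC mL growth), 12.3-14.9% (FVC % predicted growth) and 9.0-10.5% (6MWD growth).
- Power-law growth with 13 visits gives 15.8% for FVC mL.

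**5. If growth is smaller.** For DLCO and the questionnaires the growth is unknown. With four visits and power-law growth, assumed Week 52/Week 28 SD ratios of 1.00, 1.05, 1.10 and 1.20 give 5.0%, 6.2%, 7.4% and 9.7%.

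**6. Simulation check.** 600 trials per setting, four visits, 329 per arm, AR(1) correlation 0.7 and an assumed missing-at-random dropout of about 15%:

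| Model | FVC mL growth | 6MWD growth |
|---|---|---|
| Lowest-AIC equal-variance structure | 14.0% | 11.8% |
| Heterogeneous AR(1) | 6.3% | 4.2% |
| Unstructured | 6.0% | 4.3% |

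The Monte Carlo error is about 0.9 points near 5% and about 1.4 points near 14%. Heterogeneous AR(1) was the generating structure, so its result shows what letting the variances differ achieves; it does not show that AR(1) correlation is right. The unstructured fit converged in all 1,200 trials.

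**The case against.** The strongest reply is that the rule will probably never be used for the tested endpoints. Four visits need 4 × 5/2 = 10 covariance parameters with about 658 patients, and the simulated fits never failed. This stands for the global analysis of DLCO and the questionnaires. It is weaker for the FVC sensitivity model, which needs 13 × 14/2 = 91 parameters, and for the smaller China and Japan samples.

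Second, the SDs belong to other endpoints. FVC mL, 6MWD and FVC % predicted are formally tested with the random-coefficient model. The questionnaires are bounded scales and DLCO is measured on local equipment, so growth like FVC cannot be presumed. This stands, and it is why the range for these endpoints starts at 5%.

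Third, UCSD-SOBQ, SGRQ and DLCO are fifth, sixth and eighth of the nine secondaries in the fixed sequence. A formal claim is affected only if the primary and every earlier secondary test succeed. The one place where the FVC figures apply directly is a sensitivity analysis with no alpha attached. Both points stand.

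Fourth, the SDs are back-calculated from model standard errors in one arm of the earlier study, and the number of patients behind the Week 52 values is not given. Protocol 6.2.1 calls the source a random coefficient regression model; SAP 2.2.1 calls it an MMRM. They indicate growth but are not observed visit-wise SDs.

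**Conclusion.** The point holds conditionally and is minor. If the unstructured MMRM does not converge and variance grows over time, the stated fallback gives anti-conservative Week 52 inference, and the AIC choice does not cure it. Conditional on its use, type I error is about 14% for the 13-visit FVC sensitivity analysis (12-16% across the structures and growth shapes tried). For DLCO, UCSD-SOBQ and SGRQ it is about 5-15%: 5% with no growth, about 9-10% with growth like 6MWD, and about 12-15% with growth like FVC. These figures rest on an assumed growth shape, a large-sample approximation and, for the last three endpoints, borrowed growth.

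Three stronger readings are tempting, and the documents do not support them:
- That the trial runs at 9-15% type I error. The planned unstructured analysis keeps about 5%.
- That the plan's own figures show growing variance for DLCO and the questionnaires. They cover only FVC and 6MWD.
- That the primary or key secondary test is exposed. Protocol 6.5.1 does list the same structures for the primary model, but the SAP supersedes it. SAP 4.3.2, which 4.4.1 also follows, instead removes covariates and then the random slope.

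**What to change.** In SAP 4.4.2.1 and 4.3.3.1.2, replace the list and the AIC choice with a fixed order: heterogeneous Toeplitz, then heterogeneous AR(1), then heterogeneous compound symmetry, using the first that converges. If none converges, use a simpler structure with sandwich standard errors and a stated degrees-of-freedom method. SAP 4.4.2.2 and 4.7.6 then inherit the change. Make it before unblinding, so that the covariance rule cannot look data-driven.

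The cost is a few lines of SAP text and a program option; nothing changes if the unstructured model converges. There are small downsides. The new structures have more parameters: heterogeneous Toeplitz needs 4 + 3 = 7 with four visits and 13 + 12 = 25 with 13, against 4 and 13 for plain Toeplitz. Sandwich standard errors can be unreliable in small subpopulations, and they do not correct the point estimate when a wrong covariance is fitted to data with missing-at-random dropout. That is why they come last.
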